3.4.1 Sample Size for Retrospective Study Phase

(1) Sample Size for Model Training and Validation: Training Set ($n = 1,000$) and Internal Validation Set ($n = 500$)

Estimation Basis: The sample size of this phase follows empirical rules of machine learning and feasibility principles. Complex deep learning models for WSIs require a large amount of annotated data to avoid overfitting. Empirical experience shows that 1,000 to 5,000 samples are generally required for each category. This study targets four categories of treatment response classification. A sample size of 1,000 is set to balance model performance and data collection feasibility, which is consistent with the sample size of existing top-tier multimodal AI studies. The size of the internal validation set generally accounts for 20%–30% of the training set. A total of 500 samples can estimate model performance indicators (such as AUC) with a small standard error and meet the requirements of hyperparameter tuning.

(2) External Validation Set 1 ($n = 3,000$)

Estimation Basis: This phase is used for preliminary evaluation of model calibration and generalization ability, and a sufficient sample size is required to detect clinically significant declines in model performance.

a sample size of 3,000 provides sufficient statistical power to support subgroup analysis and subsequent fine-tuning of the model.

(3) External Validation Set 2 ($n = 10,000$)

Estimation Basis: This phase is for the final test of the locked model, and a high-precision estimation of performance indicators (such as AUC) is required. The sample size is calculated reversely according to the width of the AUC confidence interval.

Given $AUC = 0.80$ and the target 95% confidence interval width ≤ 0.04 (i.e., ± 0.02),

approximately 8,600 cases are required according to calculations using PASS software. A total of 10,000 cases are set to reserve sufficient margin and ensure high credibility of the results.

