Recent studies have demonstrated that the Tumor Immune Microenvironment (TIME) is a fundamental biological factor affecting the sensitivity to TACE and TKIs in HCC patients. Preoperative contrast-enhanced CT/MRI can directly reflect tumor vascularity, boundary definition, peritumoral infiltration and satellite lesions. These imaging characteristics are closely correlated with postoperative pathological findings including Microvascular Invasion (MVI) and tumor differentiation, and further determine responses to adjuvant therapy. For example, preoperative MRI radiomic features such as textual heterogeneity and irregular tumor margins have been proven to be significantly associated with postoperative HCC recurrence risk. Moreover, CT perfusion parameters can predict the degree of tumor necrosis after TACE treatment. Furthermore, the combination of preoperative imaging and postoperative pathological images enables the construction of tumor spatiotemporal evolution models to reveal dynamic biological changes before and after therapeutic intervention. Therefore, multimodal data integrating preoperative imaging, postoperative pathological images, pathological reports and clinical indicators can break the limitations of single-source data and substantially improve the accuracy of adjuvant therapy response prediction.

Breakthroughs in artificial intelligence, especially deep learning technology, have opened up a new avenue to explore in-depth pathological information from routine Hematoxylin and Eosin (H&E) stained Whole Slide Images (WSIs). As conventional postoperative pathological materials, H&E WSIs are generated for all HCC patients after surgery without additional sampling or testing. The cellular and histological details contained in WSIs can effectively reflect core characteristics of the TIME. Specifically, Convolutional Neural Networks (CNN) and Vision Transformer (ViT)

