(2) Construction and Multi-level Clinical Validation of Treatment Response Prediction Model

This is the core part of the study. Based on the quantified tumor immune microenvironment features output by the above model, combined with imaging data and essential clinical variables (such as TNM stage, Child-Pugh liver function classification and AFP level), a classification model will be built to predict patients' responses to four types of postoperative adjuvant therapy regimens: surgery alone, surgery combined with TACE, surgery combined with TACE plus systemic therapy, and surgery combined with systemic therapy alone. A strict hierarchical validation strategy will be adopted in this part.

Model Training Phase

Retrospective data from our center (n=1500) will be used. Inclusion criteria for patients in this phase: ① Histopathologically confirmed HCC; ② Underwent curative surgical resection; ③ Complete preoperative contrast-enhanced CT/MRI images, records of postoperative adjuvant therapy and follow-up data are available. Definition of treatment response: The primary endpoint is Relapse-Free Survival (RFS), and secondary endpoints include Overall Survival (OS) and Objective Response Rate (ORR). Multi-category machine learning algorithms (such as Gradient Boosting Decision Tree and Deep Neural Network) will be used for model training to output the most beneficial treatment regimen for each patient.

Internal Validation Phase

An independent validation set (n≈500, no overlap with the training set) will be randomly divided from the data of our center for preliminary evaluation of the model's discriminative performance and hyperparameter tuning to prevent overfitting.

External Validation Phase 1 (Retrospective Validation and Model Calibration)

Retrospective data (n=3000) will be collected from 8 to 10 medical centers nationwide. The main purposes of this phase are: ① To validate the model performance on larger and more heterogeneous external datasets; ② To calibrate or slightly optimize the model according to

validation results and finalize the predictive model.

External Validation Phase 2 (Large-scale Retrospective Validation)

The finalized model will be tested on a brand-new large-scale retrospective dataset (n=10,000) from 3 to 5 medical centers to further enhance the level of evidence and provide a solid basis for prospective studies.

(3) Study Population

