A total of 1,500 eligible surgical patients from our center will be enrolled and randomly divided into the model training set (n=1000) and internal validation set (n=500) at a ratio of 2:1, for model training, preliminary validation and optimization respectively. A total of 400 eligible patients have been enrolled so far, and the remaining 1,100 patients will be continuously recruited from the historical medical records of our center according to the inclusion and exclusion criteria.

A multi-center collaboration model will be adopted for external validation. ① External Validation

Set 1: A total of 3,000 retrospective cases from 8 to 10 domestic medical centers will be included for multi-center retrospective validation and model calibration, so as to verify the model's generalization ability across different institutions and conduct calibration or limited iterative optimization on the initial model. ② External Validation Set 2: A total of 10,000 retrospective cases from 3 to 5 large domestic medical centers will be included for the final test of the finalized model to fully evaluate its effectiveness and stability. Only forward validation will be performed on this dataset using the locked model without any parameter adjustment.

Part Two: Clinical Validation of Hepatocellular Carcinoma Adjuvant Therapy Prediction Model - Prospective Study

(1) Prospective Observational Study

A total of 1,000 eligible postoperative HCC patients will be consecutively enrolled from 10 to 15 medical centers. Preoperative imaging data, postoperative WSIs and clinical data will be collected and imported into the model to obtain predicted treatment regimens. No intervention will be implemented on actual clinical decisions in this phase. Researchers will record model prediction results and actual clinical decisions. Patients will be divided into the prediction-consistent cohort and prediction-inconsistent cohort according to whether the actual clinical decisions are consistent with model predictions. Long-term follow-up will be conducted to observe patients' actual prognosis, so as to evaluate the consistency between model predictions and actual outcomes, as well as the model's performance degradation in real-world settings.

(2) Study Population

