3.3 Evaluation Index System (Algorithm Performance, Clinical Utility, System Stability)

This study comprehensively evaluates the overall value of the AI model from three dimensions: algorithm performance, clinical utility and system stability.

Evaluation of Algorithm Performance

Conducted mainly during model development and validation, quantitative indicators are used to objectively assess the accuracy and robustness of the tumor immune microenvironment identification model and treatment response prediction model.

For the tumor immune microenvironment identification model: At the pixel level, Dice Similarity Coefficient (DSC) is used to evaluate the coincidence degree between segmentation results and expert annotations, and Intersection over Union (IoU) is adopted as a supplementary indicator. At the regional level, Precision, Recall and F1-Score are used to evaluate the recognition performance of specific components in the immune microenvironment.

For the treatment response prediction model: Area Under the Receiver Operating Characteristic Curve (AUC-ROC) is used to evaluate the binary classification ability of the model, and macro-average and micro-average AUC values are calculated. Accuracy, Precision, Recall and F1-Score calculated based on the confusion matrix are used to evaluate the performance of multi-classification tasks. Calibration Curve and Brier Score are used to assess the accuracy of predicted probabilities.

Evaluation of Clinical Utility

Conducted in the prospective study phase, focusing on evaluating the actual impact of the model on clinical decision-making and patient prognosis.

Primary clinical endpoints: Relapse-Free Survival (RFS), defined as the time from randomization to tumor recurrence or death from any cause. The Kaplan-Meier method is used for survival analysis, the Log-rank test is adopted for inter-group comparison, and the Hazard Ratio (HR) and its 95% confidence interval are calculated. Overall Survival (OS), defined as the time from randomization to death from any cause, is analyzed using the same statistical methods.

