Fairness assessment: Comprehensive fairness evaluation is carried out to analyze whether there are significant differences in model performance across subgroups divided by demographic characteristics (gender, age) and clinical characteristics (tumor stage, etiology, liver function classification). Core evaluation indicators include inter-group AUC difference, balanced odds and fairness metrics for sensitive attributes. If performance discrimination of the model is found in specific subgroups, algorithm correction will be performed to ensure the fairness of algorithm decisions. All fairness evaluation results will be fully disclosed in the research report.

Bias control in statistical analysis phase: Multivariate Cox regression model and Logistic regression model are used to adjust for known prognostic factors (such as TNM stage, vascular invasion and AFP level) to accurately estimate the independent predictive efficacy of the AI model and control potential residual confounding bias.

3.6 Data Governance System (Data Collection, Transmission, Storage Security Control; Full-chain Data Recording)

A sound data governance system is established to ensure the quality, security and compliance of data throughout the research process, covering all links including data collection, transmission, storage, processing, analysis and archiving, forming a complete data management closed loop.

Standardized data collection: Detailed Standard Operating Procedures (SOPs) for data collection are formulated to clarify the definition, format and collection specifications of all types of data. Structured electronic Case Report Forms (eCRFs) are used for clinical data collection with built-in logic verification and range check functions to ensure the accuracy and completeness of data collection. Pathological image data collection follows digital scanning standards with a unified scanning resolution of 0.25 μ m/pixel and file format of SVS. Equipment calibration and quality control tests are conducted before each batch of scanning. Laboratory test data are directly collected by docking with the Laboratory Information System (LIS) to avoid manual transcription errors.

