Random (MCAR); multiple imputation is used for data Missing at Random (MAR); selection models are applied for data Missing Not at Random (MNAR). Sensitivity analysis is conducted to compare results obtained by different missing data processing methods.

Definition of statistical analysis datasets:

Full Analysis Set (FAS): Includes all randomized patients who received at least one efficacy assessment, analyzed according to the Intention-To-Treat (ITT) principle.

Per-Protocol Set (PPS): Includes patients who fully complied with the research protocol, excluding patients with major protocol violations.

Safety Set (SS): Includes all patients who received at least one treatment, used for safety evaluation.

Primary analysis is based on the FAS, and the PPS is used for sensitivity analysis to verify the robustness of results.

Statistical methods for primary outcome indicators: For categorical variables (such as treatment response grouping), weighted F1-score and macro-average AUC are taken as main evaluation indicators, and Cohen's Kappa coefficient is used to assess the consistency between model predictions and actual clinical conditions. For survival data (RFS and OS), the Kaplan-Meier method is used to draw survival curves, the Log-rank test is used for inter-group comparison, and the Cox proportional hazards regression model is established to calculate the Hazard Ratio (HR) and its 95% confidence interval while adjusting for potential confounding factors such as age, gender and TNM stage.

Statistical methods for secondary outcome indicators: Decision Curve Analysis (DCA) is used to evaluate the clinical net benefit of the model. Calibration Curve and Brier Score are used to assess the accuracy of predicted probabilities. Repeated-measures Analysis of Variance is used for inter-group comparison of continuous variables. The Mann-Whitney U test is adopted for ordinal variables such as physician adherence and decision confidence scale scores.

Algorithm stability evaluation: Bootstrap sampling (1,000 repetitions) is used to calculate the 95% confidence interval of model performance indicators for stability assessment. SHapley Additive exPlanations (SHAP) values are used to analyze feature importance and improve model interpretability. Intraclass Correlation Coefficient (ICC) is calculated to evaluate the consistency of the model across different centers; $ICC > 0.75$ is regarded as good consistency.

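### No validation phase compares the multimodal model with a clinical-variables-only model, so the planned measures cannot show whether slides and CT/MRI add accuracy

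*Protocol*

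**What the plan says.** The Study Background states that multimodal data "can break the limitations of single-source data and substantially improve the accuracy of adjuvant therapy response prediction".

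Section 3.1, Part One (2), builds the response model from slide-derived features "combined with imaging data and essential clinical variables (such as TNM stage, Child-Pugh liver function classification and AFP level"). Section 3.2 repeats these clinical inputs and adds pathology-report text.

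The measures in Section 3.3 are for that single model: "Area Under the Receiver Operating Characteristic Curve (AUC-ROC) is used to evaluate the binary classification ability of the model", with macro and micro averages, then confusion-matrix measures, and "Calibration Curve and Brier Score are used to assess the accuracy of predicted probabilities". Section 3.8 takes weighted F1 and macro-average AUC as the main indicators and adds kappa and decision curve analysis, again with no second model.

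Section 3.4.1 sizes Set 2 on one AUC: "This phase is for the final test of the locked model, and a high-precision estimation of performance indicators (such as AUC) is required". Section 3.1 adds: "Only forward validation will be performed on this dataset using the locked model without any parameter adjustment".

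Three items bear on added value:

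- Section 3.5 plans Cox and logistic models with TNM stage, vascular invasion and AFP as example adjusters, "to accurately estimate the independent predictive efficacy of the AI model".
- Section 3.8 states that "SHapley Additive exPlanations (SHAP) values are used to analyze feature importance and improve model interpretability".
- Section 3.1, Part Two, randomises 600 patients between AI-assisted and standard decision-making.

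**The concern.** The claim in the Background is comparative, and the planned evaluation is not. Because the full model contains strong clinical predictors, its AUC, F1 and Brier score mix their contribution with that of slides and CT/MRI. A model that drew all its accuracy from the clinical inputs could report the same values as one in which the images did real work.

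The practical question is whether digital scanning, the stain-specific networks and image segmentation are worth deploying, or whether a score from routine data would do as well. The timing also matters. Set 2 is reserved for a locked model, and Section 3.8 labels post-hoc analyses exploratory. A comparator thought of after Set 2 has been opened could not confirm the claim.

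**Working it through.** **1. The plan's own figure.** Section 3.4.1 gives about 8,600 cases for AUC 0.80 with a 95% interval of ±0.02. The outcome prevalence is not stated, so the figure cannot be reproduced from the text. With the Hanley–McNeil variance, ±0.02 needs 1,880 cases at 50% prevalence, 2,645 at 30%, 7,120 at 10% and 8,820 at 8%; 8,600 corresponds to about 8.2%. However it was derived, it is a precision target for one model and does not address a difference between two.

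**2. Can standalone measures reveal that images add nothing?** A simulation of 10,000 patients used assumed log-odds coefficients: intercept −0.5, TNM 0.9, vascular invasion 0.8 (30% of patients), AFP 0.7, Child-Pugh 0.5, and zero for slides and imaging. Prevalence came out at 45%. The image-free score had AUC 0.784, close to the planning value of 0.80. The AUC alone does not expose the missing contribution.

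**3. Does the Section 3.5 adjustment reveal it?** Logistic models adjusted for TNM, vascular invasion and AFP:

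- Image-free score built only from those three variables (assumed coefficients 1.0, 0.9 and 0.8; mean AUC 0.792): significant at 0.05 in 2.5% of 400 runs. The adjustment correctly finds nothing.
- Image-free score that also carries Child-Pugh (the score in step 2): adjusted coefficient 1.02, p about 2×10⁻⁹⁸. The score looks independent, although the images add nothing.

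The safeguard works only if every clinical input to the model is among the adjusters. Child-Pugh is an input (Sections 3.1 and 3.2) but is not named as an adjuster in Section 3.5, or in Section 3.8, where the examples are age, gender and TNM stage.

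**4. Is Set 2 large enough for a direct comparison?** Single-AUC variance, with A = 0.80, Q1 = A/(2−A) = 0.6667 and Q2 = 2A²/(1+A) = 0.7111:

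Var = [A(1−A) + (n₁−1)(Q1−A²) + (n₀−1)(Q2−A²)] / (n₁n₀)

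At n=10,000 and 50% events: (0.16 + 4,999×0.02667 + 4,999×0.07111) / 25,000,000 = 1.956×10⁻⁵, so SE = 0.0044.

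For two models on the same patients, SE(difference) = √(2(1−r))×SE. The difference detectable at 80% power, two-sided 0.05, is (1.960+0.842)×SE(difference). The correlation r and the event proportion are assumptions.

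| n | Events | r=0.5 | r=0.7 | r=0.9 |
|---|---|---|---|---|
| 10,000 | 50% | 0.0124 | 0.0096 | 0.0055 |
| 10,000 | 30% | 0.0147 | 0.0114 | 0.0066 |
| 10,000 | 10% | 0.0241 | 0.0187 | 0.0108 |
| 1,000 | 50% | 0.0392 | 0.0304 | 0.0175 |
| 1,000 | 30% | 0.0465 | 0.0360 | 0.0208 |

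Set 2 can carry the comparison. The observational cohort of 1,000 can only support it.

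**5. Half-width is not power.** At 35% events and r=0.5 the 95% half-width is 1.96×0.0049 = 0.0097. A true gain of 0.01 then has power of about Φ(0.01/0.0049 − 1.96), roughly 50%. The 80%-power figures in the table are the ones to plan on.

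**The case against.** The strongest reply is that this is an omission, and that ablation or comparator models could sit in a separate SAP that is not shown. The Background sentence is motivation, not a hypothesis, and contrasts multimodal with single-source data; no endpoint claims superiority over a clinical score. That stands as a reason to call this an improvement. It does not remove the point. The comparator must be trained and locked before Set 2 is opened, and clinical indicators are one of the sources that the Background says are improved on.

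A reader might infer that a system whose images add nothing would pass every stated measure. The document does not support that wording: no pass mark is set for AUC, F1 or Brier score, and the only threshold is an ICC above 0.75 for consistency across centres. Dice, IoU and regional F1 also test the slide component against expert annotation, although they show that tissue is read correctly, not that reading it improves prediction.

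A reader might also infer that the premise goes wholly untested. That is too strong. The Section 3.5 adjustment addresses independent value, its list of factors is open, and step 3 shows that it works when the list is complete. The randomised trial does test clinical utility against standard practice. But a significant adjusted coefficient gives no increment in AUC or Brier score, the trial cannot separate images from clinical inputs, and SHAP describes the fitted model without testing added accuracy.

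**Conclusion.** The point holds as a cheap improvement. No phase names a clinical-only model or a difference in AUC, C-index or Brier score, so the planned measures cannot show whether slides and CT/MRI add accuracy. The existing safeguards cover this in part and should be credited.

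The 10,000 patients already planned would detect a gain of about 0.006 to 0.015 at 30% to 50% events, or 0.011 to 0.024 at 10%. These figures rest on an assumed correlation of 0.5 to 0.9, both AUCs near 0.80, an unstated prevalence, independent patients, and a binary AUC standing in for the four-regimen macro-average. It should not be inferred that a gain of 0.01 is resolved in all these settings.

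**What to change.** - **Comparator.** On the same 1,000 training patients, fit a model with every clinical and pathology-report input of the full model, but no slide (H&E or IHC) or imaging features. Name Child-Pugh explicitly: the data list in the Section 3.1 eligibility criteria does not mention it, and leaving it out would let the full model win without help from the images.
- **Equal treatment.** Give it the same Set 1 calibration as the full model, and lock both together before Set 2 is opened.
- **Analysis.** In Set 2, prespecify the paired difference in macro-average AUC and Brier score with a 95% confidence interval. Resample patients within centre and show per-centre results; 3 to 5 centres are too few for a cluster bootstrap. Treat the 1,000-patient observational cohort as supportive.
- **Claim.** State that multimodal data improve prediction only if the interval for the AUC difference lies above zero. Always report the size of the gain, because a trivial difference can be significant at this sample size and the Background promises a substantial one.

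The cost is extra model fits and a few sentences of plan text, with no new patients. The downside is that the reported gain may look less favourable than an absolute AUC.
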